**Minor**
**One of the following:**

- Cardiac structure\* perforation, injury, or compromise *not* resulting in death, VARC type  $\geq 2$  bleeding, haemodynamic compromise or tamponade, or requiring unplanned surgical or percutaneous intervention
- New pericardial effusion *not* resulting in death, VARC type  $\geq 2$  bleeding, haemodynamic compromise or tamponade, or requiring unplanned surgical or percutaneous intervention
- Coronary obstruction *not* resulting in death, haemodynamic compromise, myocardial infarction, or unplanned surgical or percutaneous intervention
- Coronary artery access difficulties for needed coronary angiography or intervention, *not* resulting in death, haemodynamic compromise, myocardial infarction, coronary or aortic root injury, compromise in aortic valve prosthesis integrity, unplanned surgical or percutaneous intervention, or the inability to perform the intended procedure

\*Aortic annulus, left ventricular outflow tract, ventricular septum, left or right ventricle, atrial septum, left or right atrium, mitral valve apparatus, tricuspid valve apparatus, coronary artery, and coronary sinus. Also includes any new inter-cardiac cavity communication (e.g. VSD), and new left-to-right or right-to-left shunt.

†Angiographic or echocardiographic evidence of a new partial or complete obstruction of a coronary ostium or an epicardial coronary artery, either by the valve prosthesis itself, the native leaflets, embolized material (e.g. calcification, thrombus, and/or tissue), external device compression, or the consequence of coronary artery instrumentation (e.g. dissection, occlusion, embolization), occurring during or after the procedure, and with objective evidence of ischaemia (i.e. new ST-segment deviation on electrocardiogram) or symptoms. Excludes coronary complications due to a concomitant or subsequent planned percutaneous intervention for significant coronary artery disease.

**TABLE 8** Other acute procedural and technical valve-related complications\*

**Conversion to open surgery**

Conversion to open sternotomy or thoracotomy using cardiopulmonary bypass secondary to any procedure-related complication or failed intended transcatheter approach. Should be classified as:

- *Intraprocedural conversion*: during the index procedure
- *Periprocedural conversion*:  $\leq 30$  days after the index procedure
- *Delayed conversion*:  $> 30$  days after the index procedure

**Unplanned use of mechanical circulatory support†**
**Implantation of multiple (>1) transcatheter valves during the index hospitalization**
**Valve malposition**

Should be classified as:

- *Valve migration*: After initial correct positioning, the valve prosthesis moves upward or downward, within the aortic annulus from its initial position, without valve embolization
- *Valve embolization*: The valve prosthesis moves either upward or downward after final deployment such that it loses contact with the aortic annulus
- *Ectopic valve deployment*: Irretrievable deployment of a valve prosthesis at a site other than the intended position because of valve embolization or inability to deliver the prosthesis to the desired location

**Paravalvular regurgitation (see Table 16)**

\*Individual events should be collected so that specific event rates can be determined.

†Mechanical circulatory support includes: cardiopulmonary bypass (CPB), extracorporeal membrane oxygenation (ECMO), transcatheter pumps (e.g. Impella) or intra-aortic balloon pump (IABP).

For the specific purpose of the present study, the following periprocedural complications that occur in the first 72 hours after TAVI are considered actionable by emergent cardiac surgery:

- Severe aortic regurgitation with clinical instability
- Valve embolization into the left ventricle
- Valve migration with concomitant and refractory haemodynamic instability
- Aortic dissection
- Aortic perforation
- Aortic rupture
- Annular rupture
- Perforation of the left ventricle
- Coronary obstruction (that cannot be managed by percutaneous intervention)
- Ventricular septal perforation
- New damage (chordae papillary muscle, or leaflet) to the mitral valve apparatus or dysfunction (e.g., restrictions due to THV) of the mitral valve.

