**undergoing ECS were still high (45.8% at 30-days follow-up)** [12]. An interim analysis from the all-comer – prospectively collected German Aortic Valve Registry (GARY) analyzed intra- and post-procedural complication rates during TAVI in patients treated from 2011 to 2013. The analysis included 15,964 patients, 70.7% of whom were performed by transfemoral approach. **Urgent sternotomy was required in 201 (1.3%) patients, 61 (30.3%) of these patients underwent TAVI using a transapical approach. In-hospital mortality was 42.3% for patients requiring ECS in comparison to 5.2% in the overall population ( $p < 0.05$ ).** Over time, there was a numerical, not statistically significant, decline in the need for urgent sternotomy from 1.6% in 2011 to 1.1% in 2013 ( $p = 0.13$ ). Univariate and multivariate analysis failed to identify any predictor of the occurrence of emergent cardiac surgery during TAVI, although patients who required cardiac surgery were more likely to undergo emergent TAVI, had higher rates of general anesthesia, longer procedural time, and a greater degree of aortic insufficiency after valve implantation. This study might not reflect current practice, since the transapical approach is seldom used nowadays [13]. A more contemporary study analyzed predictors and outcomes of ECS in 1775 TAVI patients treated from 2011 to 2016 in a single-center high-volume hospital. Over five years, 32 (2.1%) of patients required conversion to open cardiac surgery. **The conversion rates to open surgery decreased over time, from 6% in 2011 to 1% in 2016.** The most common cause of ECS was pericardial tamponade in 47% of cases, followed by valve embolization (28%) and annular rupture (16%). **Mortality at 30-day and 1-year in patients requiring urgent cardiac surgery was high 44% and 59.3%.** The authors found no baseline or procedural related predictors for ECS in their analysis. Of note, rates of conversion to open surgery according to access approach transfemoral vs transapical were not specified [14]. Eggebrecht et al. published an independent, international, and multicenter trial of 27,760 transfemoral TAVI from 79 centers, analyzing outcomes of patients requiring ECS during TAVI. Procedures were performed over the years 2013 to 2016, and the need for ECS widely varied across centers ranging from 0% to 6.7%. **In 25 centers, performing TAVI in 3821 (13.3%) patients, not even a single case required salvage surgery during TAVI interventions.** Overall, the rates for emergent cardiac surgery were 0.76% and significantly decreased from 1.07% in 2013 to 0.68% and 0.73% in 2015 and 2016, respectively. The most frequent causes for ECS were left ventricular perforation, annular rupture, and valve embolization/migration in 28%, 21%, and 13% of patients, respectively. **Immediate post-procedural mortality was 34% and at one-year follow-up only 22% of patients were alive.** Older age (>85-year-old) and annular rupture were independent predictors of mortality in multivariate analysis. **The rates of emergent surgery were similar whether patients were treated in high-volume versus low-volume centers.** *The authors concluded that although rare, ECS for the salvage of complicated transfemoral TAVI carries a grim prognosis with survival rates at 1-year follow-up below 25%. Thus, the Authors recommend that prevention of complications should be the main strategy to improve outcomes in patients undergoing transfemoral TAVI* [15]. To date, the largest study reporting ECS during TAVI analyzed data of all 47,546 patients who underwent TAVI between the years 2011–2015 in the

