### 4.3 Primary safety endpoint

- Death due to periprocedural complications actionable by emergent cardiac surgery

To test whether mortality due to periprocedural complications actionable by emergent cardiac surgery differs between the TAVI procedures performed in the center without on-site cardiac surgery and the TAVI procedures performed by the same team in the center with on-site cardiac surgery.

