### 8.14 Emergent cardiac surgery for periprocedural complications

It is defined as any cardiothoracic surgical intervention with cardiopulmonary bypass for periprocedural complications (see paragraph 8.13) requiring urgent aortic valve replacement, repair of myocardial or aortic injury, or pericardial drainage performed within the first 72 hours after TAVI.

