### 8.15 Death due to periprocedural complications actionable by emergent cardiac surgery

It is defined as any death associated with periprocedural complications actionable by emergent cardiac surgery (see paragraphs 8.13 and 8.14). The occurrence of this endpoint will be considered both in cases where emergent cardiac surgery was not performed and in cases where it is performed but with lethal outcome.

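### The closed list behind the primary safety endpoint omits right-heart and atrial perforation, and tamponade without a listed source, although section 8.14 counts operations that would treat them

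*Protocol*

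**What the plan says.** Protocol section 4.3 names the primary safety endpoint: "Death due to periprocedural complications actionable by emergent cardiac surgery". Section 8.15 defines it as any death associated with such a complication, refers to 8.13 and 8.14 for the meaning, and counts the death whether or not surgery was performed.

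Section 8.13 first reproduces the VARC-3 tables and then sets a study-specific list, stating that "the following periprocedural complications that occur in the first 72 hours after TAVI are considered actionable by emergent cardiac surgery". Eleven items follow, with no catch-all. The injuries to heart or aortic structures are aortic dissection, perforation and rupture, annular rupture, "Perforation of the left ventricle", ventricular septal perforation and mitral apparatus damage. The other items concern severe regurgitation, valve embolization, valve migration and coronary obstruction.

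Section 8.14 defines emergent cardiac surgery by reference to 8.13 and includes "urgent aortic valve replacement, repair of myocardial or aortic injury, or pericardial drainage performed within the first 72 hours after TAVI".

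Tamponade appears elsewhere as one of the other safety endpoints (section 4.4). Its definition in section 8.22 does not depend on which structure was injured. In the background (section 2.4), one single-center series is summarized thus: "The most common cause of ECS was pericardial tamponade in 47% of cases".

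**The concern.** A primary safety endpoint meant to capture deaths that emergent surgery might have averted should cover the complications that the protocol itself treats as surgically actionable. The 8.13 list does not do so fully. A patient who dies of tamponade after right-ventricular or atrial perforation, or of tamponade with no source found, has no listed complication. Section 8.14 nevertheless names drainage of the pericardium and repair of heart muscle among the operations that count.

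Because 8.15 points to both sections, the adjudication committee could exclude the death (by the list) or include it (by the operations that would address it). Section 7.7 makes its rulings binding. Section 7.8 has the DSMB monitor complications requiring emergent surgery against a 2% limit, and that count could inherit the same uncertainty. The comparison rests on very few events, so the classification of a single death matters.

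**Working it through.** **Step 1. Set the sections side by side.**

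| Complication | VARC-3 tables in 8.13 | Study list in 8.13 | Operation named in 8.14 |
|---|---|---|---|
| Left-ventricular perforation | yes | yes | myocardial repair, drainage |
| Annular or aortic rupture, aortic perforation | annulus in the cardiac-structure table; aortic rupture in the vascular table of 8.20 | yes | aortic repair, drainage |
| Right-ventricular perforation | yes (table footnote) | no | myocardial repair, drainage |
| Atrial perforation | yes (table footnote) | no | myocardial repair, drainage |
| Pericardial effusion or tamponade, no source identified | yes (separate major item) | no | drainage |

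The last column shows which named operation types could apply. Section 8.14 does not itself pair operations with injuries.

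**Step 2. Separate what is captured from what is not.** Section 8.15 uses the broad link of association, so a tamponade death caused by a listed injury is counted through that injury. Only tamponade or perforation deaths with an unlisted or unidentified source are left out.

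**Step 3. Expected number of primary safety events.** The protocol states no expected count. Section 2.6 illustrates that 10 of 1,000 patients need emergent surgery, that half of them are saved with on-site surgery, and that all die without it. Section 9.1 gives 187 control and 373 experimental patients.

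- Control: 187 × 0.01 × 0.5 = 0.94 deaths, or 0.50%.
- Experimental: 373 × 0.01 × 1.0 = 3.73 deaths, or 1.00%.
- Implied difference: 0.50 percentage points.

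The need-for-surgery rate can be varied over figures in the protocol while keeping the same fatality assumption:

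| Rate needing surgery | Source | Control deaths | Experimental deaths |
|---|---|---|---|
| 0.76% | transfemoral registry, section 2.4 | 187 × 0.0076 × 0.5 = 0.71 | 373 × 0.0076 = 2.83 |
| 1% | illustration, section 2.6 | 0.94 | 3.73 |
| 2% | DSMB limit, section 7.8 | 187 × 0.02 × 0.5 = 1.87 | 373 × 0.02 = 7.46 |

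**Step 4. Weight of one reclassified death, at the 1% rate.**

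- One experimental death: 1/373 = 0.27 points. If it is not counted, (3.73 − 1)/373 = 0.73%, and the difference falls from 0.50 to 0.73 − 0.50 = 0.23 points.
- One control death: 1/187 = 0.53 points, about as large as the whole implied difference.

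**Step 5. How many deaths could be affected?** The documents do not say. The 47% in section 2.4 is a share of operations, not deaths, and does not separate tamponade by source. The affected number may be zero.

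**The case against.** The strongest reply is that the list was narrowed on purpose. It is introduced as specific to this study, directly after the broader VARC-3 tables, and it is organized mainly by injured structure, with tamponade as a consequence. This explains why most tamponade deaths are captured. It gives no reason for leaving out the right ventricle, the atria or an unidentified source.

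A second reply is that these deaths are not lost: they enter the primary composite as all-cause death, and tamponade is reported separately. That is true, but it does not repair the primary safety endpoint.

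Four stronger readings are tempting and are not supported.

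- **That 8.13 and 8.14 contradict each other outright.** They do not. Drainage and myocardial repair can be read as treatment of injuries already on the list. The defect is a gap and an ambiguity.
- **That the bypass requirement in 8.14 removes deaths from the endpoint.** It does not. Section 8.15 is triggered by the complication and counts deaths with or without surgery. The requirement bears on the count of emergent operations only.
- **That 47% of the expected experimental deaths would be missed** (0.47 × 3.73 = 1.75). That series did not specify conversion rates by access route, whereas this trial is transfemoral only. Its three named causes sum to 47 + 28 + 16 = 91%, so at most 9% is left for left-ventricular perforation outside the tamponade group; the 47% may well include injuries already listed. The product also treats every tamponade as fatal, while section 2.7 reports two treated successfully by pericardiocentesis.
- **That the omission demonstrably biases the comparison towards no difference.** The list applies equally to both arms, and no arm-specific rates are given. That direction is plausible if lack of on-site surgery raises mortality from these injuries, but it is not shown.

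**Conclusion.** The point holds as a gap in the endpoint definition. Followed literally, section 8.13 excludes deaths from right-ventricular or atrial perforation, and from tamponade without an identified listed source. Section 8.14 suggests that the same deaths are surgically actionable, so adjudication could go either way.

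The number of such deaths is unknown and may be zero. The importance comes from how few events the endpoint will have: about 0.9 control and 3.7 experimental at the 1% rate, and 0.7 to 1.9 control and 2.8 to 7.5 experimental over rates of 0.76% to 2%. These counts rest on the rough fatality assumptions of section 2.6 (half with on-site surgery, all without). At the 1% rate, one uncounted experimental death would roughly halve the implied difference. The primary efficacy endpoint and the sample size are unaffected.

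**What to change.** Reconcile sections 8.13, 8.14 and 8.15 before adjudication begins. Add one item to the endpoint list in 8.13: perforation of any cardiac chamber, or cardiac tamponade, not manageable percutaneously. This follows the form of the existing coronary-obstruction item. Leave the left-ventricular item as it stands so that the addition does not narrow it. Carry the same wording into the adjudication charter and into the complication count monitored by the DSMB. If exclusion was intended, say so in 8.13, give the reason, and limit drainage and myocardial repair in 8.14 explicitly to listed injuries.

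The cost is a slightly broader endpoint, a definition edit and a small charter update. No new data are needed, because tamponade is already collected under section 4.4.

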### 8.14 Emergent cardiac surgery for periprocedural complications

It is defined as any cardiothoracic surgical intervention with cardiopulmonary bypass for periprocedural complications (see paragraph 8.13) requiring urgent aortic valve replacement, repair of myocardial or aortic injury, or pericardial drainage performed within the first 72 hours after TAVI.

### 8.15 Death due to periprocedural complications actionable by emergent cardiac surgery

It is defined as any death associated with periprocedural complications actionable by emergent cardiac surgery (see paragraphs 8.13 and 8.14). The occurrence of this endpoint will be considered both in cases where emergent cardiac surgery was not performed and in cases where it is performed but with lethal outcome.

## 8.16 Myocardial infarction

**TABLE 11 Myocardial infarction (adapted from 4th Universal, SCAI and ARC-2 definitions)**
**Type 1 (Spontaneous MI) (>48 h after the index procedure)\***

- Detection of a rise and/or fall of cTn values with at least one value above the 99th percentile URL with at least one of the following:
  - Symptoms of acute ischaemia
  - New ischaemic ECG changes (new ST-segment or T-wave changes or new LBBB)
  - New pathologic Q-waves in  $\geq 2$  contiguous leads
  - Imaging evidence of a new loss of viable myocardium or new wall motion abnormality in a pattern consistent with an ischaemic aetiology
  - Identification of a coronary thrombus by angiography or autopsy
- Post-mortem demonstration of an atherothrombus in the artery supplying the infarcted myocardium, or a macroscopically large circumscribed area of necrosis with or without intramyocardial haemorrhage, meets the type 1 MI criteria regardless of cTn values

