
Exclusion criteria
	
 
1. Unsuitable for transfemoral TAVI
 
2. Emergent TAVI
 
3. Noncardiovascular comorbidity reducing life expectancy to <1 year
 
4. Any factor precluding 1-year follow-up
 
5. Refusal informed consent
 

Primary endpoint
	
One-year cumulative occurrence of all-cause death, stroke and hospital readmission for cardiovascular causes
 
The adverse events will be collected from the time of randomization, also considering adverse events during the waiting time for the TAVI procedure.

Secondary efficacy endpoints
	
 
• All-cause death
 
• Cardiovascular death
 
• Myocardial infarction
 
• Hospital admission for cardiovascular cause
 
• Hospital admission for heart failure
 
• Cerebrovascular accident
 
• Ischemic stroke
 

	
 
• Hospital admission for pneumonia (<math>\pm</math> respiratory failure)
 
• Need for balloon aortic valvuloplasty for emergent condition
 
• Quality of life measured with the Eq-5D and KCCQ-12 scales
 
• Time spent on the waiting list before TAVI
 

Primary safety endpoint	Death due to periprocedural complications that can be addressed with emergent cardiac surgery
Other safety endpoints	
 
• Cardiac tamponade
 
• Bleeding
 
• Kidney failure (requirement of renal replacement therapy)
 
• Severe aortic regurgitation (aortic regurgitation according to current guidelines)
 
• Multiorgan failure (failure of at least two organ systems)
 
• Vascular access site and access related complications
 
• Conduction disturbances and arrhythmias
 
• Endocarditis
 
• Valve thrombosis
 
• Valve malpositioning
 
• Valve embolization
 
• Ectopic valve deployment
 
• TAV-in-TAV deployment
 

Assessment Schedule	Pre-eligibility screening, inclusion, randomization, TAVI, 1-month visit after TAVI, 6-month visit after TAVI, 12-month visit after TAVI, and every 12 months thereafter.
Study Duration	Enrollment will occur over approximately 2 years with an expected minimum follow-up of 12 months. All patients will be followed until 3 years.

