### 4.2 Secondary efficacy endpoints

- All-cause death
- Cardiovascular death
- Myocardial infarction
- Hospital admission for cardiovascular cause
- Hospital admission for heart failure
- Cerebrovascular accident
- Ischemic stroke
- Hospital admission for pneumonia ( $\pm$  respiratory failure)
- Need for balloon aortic valvuloplasty for emergent condition
- Quality of life measured with the Eq-5D and KCCQ-12 scales
- Time spent on the waiting list before TAVI

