## 5.6 Measures to minimize/avoid bias

The trial is open-label. Despite the obvious benefits of a double-blind design, the hospital where the TAVI intervention is performed cannot be concealed to the operator or the patient. An independent Clinical Event Committee (CEC) will adjudicate all endpoints. The CEC members and the CEC management team will be completely blinded to the randomization, as well as patient identifying information. The CEC will adjudicate the events based on predetermined definitions outlined below (VARC-3 consensus document). Other measures to avoid or minimize bias introduced by the open-label design will include intent-to-treat principles of analysis and use of objective measures for endpoint classification. An additional bias can be that some patients may receive a valve type different from that declared at the time of the randomization. This bias may occur as a consequence of factors and/or variables that emerged after randomization and immediately before the procedure or during the procedure itself. Being crucial that the distribution of self-expandable or balloon-expandable valves would be similar between study groups (despite current literature not reporting significant difference in the outcomes in the comparison of self-expandable vs. balloon-expandable), these data will be strictly monitored and eventual correction to the randomization list will be applied to avoid any unbalance. The Academic Research Organization staff will monitor the type and brand of the valve. This activity will be independent and with the aim of guaranteeing the equal distribution of valves between study arms. Any potential bias and difference will be reported by the ARO team to DSMB, which will be in charge to decide and to suggest possible corrective maneuvers.

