**Type 2 (Imbalance between myocardial oxygen supply and demand)\***

- Detection of a rise and/or fall of cTn values with at least one value above the 99th percentile URL, and evidence of an imbalance between myocardial oxygen supply and demand unrelated to coronary thrombosis, requiring at least one of the following:
  - Symptoms of ischaemia
  - ECG changes indicative of new ischaemia (new ST-segment or T-wave changes or new LBBB)
  - New pathologic Q-waves in  $\geq 2$  contiguous leads
  - Imaging evidence of a new loss of viable myocardium or new wall motion abnormality

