**Type 3 (MI associated with sudden cardiac death)\***

- Patients who suffer cardiac death, with symptoms suggestive of myocardial ischaemia accompanied by presumed new ischaemic ECG changes or ventricular fibrillation but die before blood samples for biomarkers can be obtained, or before increases in cardiac biomarkers can be identified, or MI is detected by autopsy examination.

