**Type 5 Peri-procedural (post-SAVR, TAVR or CABG) MI ( $\leq 48$  h after the index procedure)‡**

- **In patients with normal baseline CK-MB:** The peak CK-MB measured within 48 h of the procedure  $\geq 10 \times$  the local laboratory ULN or CK-MB  $\geq 5 \times$  ULN with one or more of the following:
  - New pathologic Q-waves in  $\geq 2$  contiguous leads
  - New persistent LBBB‡
  - Flow-limiting angiographic complications in a major epicardial vessel or  $>1.5$  mm diameter branch
  - Substantial new loss of viable myocardium on imaging related to the procedure
- In the absence of CK-MB measurements and a normal baseline cTn, a cTn (I or T) level measured within 48 h of the procedure rises to  $\geq 70 \times$  the local laboratory ULN or  $\geq 35 \times$  ULN with one or more of the following:
  - New pathologic Q-waves in  $\geq 2$  contiguous leads
  - New persistent LBBB‡
  - Flow-limiting angiographic complications in a major epicardial vessel or  $>1.5$  mm diameter branch
  - Substantial new loss of viable myocardium on imaging related to the procedure
- **In patients with elevated baseline CK-MB (or cTn):** The CK-MB (or cTn) rises by an absolute increment equal to those levels recommended above from the most recent pre-procedure level plus new ECG changes as described.

The use of high-sensitivity (hs)-troponins is recommended for diagnosis of spontaneous MI, but has not been studied for assessment of peri-procedural MI. Standard troponin assays are therefore recommended for evaluation of peri-procedural MI. Peri-procedural biomarker elevation  $>ULN$  not meeting the criteria for MI should be categorized as 'myocardial injury not meeting MI criteria'.

\*Adapted from Thygesen *et al.* (169).

†Adapted from Moussa *et al.* (167) and Garcia-Garcia *et al.* (168).

‡LBBB criteria to be used with caution after TAVR or SAVR given the relatively high rate of new LBBB after these procedures.

CK-MB = creatine kinase-MB; cTn, cardiac troponin; ECG = electrocardiogram; LBBB = left bundle branch block; MI, myocardial infarction; SAVR = surgical aortic valve replacement; TAVR = transcatheter aortic valve replacement; ULN = upper limit of normal; URL = upper reference limit.

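### Table 11 has no category for a non-fatal, non-stent spontaneous MI before TAVI, so a larger proportion of such events would go uncounted in the arm that waits longer

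*Protocol*

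**What the plan says.** "Myocardial infarction" is listed without qualification among the secondary efficacy endpoints in section 4.2. The definition is Table 11 in section 8.16, which dates its spontaneous category from the procedure: "Type 1 (Spontaneous MI) (>48 h after the index procedure".

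On the clock, the synopsis states under the primary endpoint: "The adverse events will be collected from the time of randomization, also considering adverse events during the waiting time for the TAVI procedure". Section 9.1 repeats that events between randomization and TAVI count, and section 7.6 requires all adverse events to be reported.

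On adjudication, section 5.6 says: "The CEC will adjudicate the events based on predetermined definitions outlined below (VARC-3 consensus document". Section 7.7 makes the committee's results binding for the final analysis and leaves its working rules to a charter that is not at hand.

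Section 8.12 deals with the same mismatch for hospitalization. It notes that the consensus definition looks at the time after the procedure, and it widens that definition because this trial also studies the wait. Section 8.16 makes no such adaptation.

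**The concern.** The table was written for follow-up that starts at the procedure, whereas this trial starts its clock at randomization, weeks or months earlier. An infarction with a troponin rise, ischaemic ECG changes and coronary thrombus in the sixth week of the wait satisfies the Type 1 diagnostic criteria but falls outside the Type 1 time window.

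The uncovered interval differs between the arms. Controls join the referring center's waiting list (synopsis, study arms), and the rationale in sections 2.6 and 3 is that treatment without on-site surgery shortens the wait. A literal reading therefore discards part of the waiting-time harm that the trial wants to see, and a larger share of it in the control arm. Section 9 promises multiplicity control that extends to the secondary endpoints, so the MI comparison is not plainly descriptive.

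**Working it through.** **Step 1. Does any category cover a spontaneous MI between randomization and TAVI?**

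| Category in Table 11 | Time window | Covers it? |
|---|---|---|
| Type 1, spontaneous | more than 48 h after the index procedure | No, fails the window |
| "Type 2 (Imbalance between myocardial oxygen supply and demand" | none stated | No, must be unrelated to coronary thrombosis |
| Type 3, sudden cardiac death | none stated | Fatal cases only (includes "or MI is detected by autopsy examination") |
| Type 4A, PCI-related | 48 h or less after the procedure | No |
| Types 4B and 4C | timed from the stent, or not timed | Stent thrombosis or restenosis only |
| "Type 5 Peri-procedural (post-SAVR, TAVR or CABG) MI" | 48 h or less after the procedure | No |

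What is left without a category is the non-fatal, non-stent-related Type 1 MI before TAVI.

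**Step 2. Proportion uncounted and apparent ratio.** The plan gives no figure to reproduce on this point.

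Inputs from the protocol: waits of 2 to 6 months in Italy (2.5), and the supposition that the wait is halved (2.6). Assumptions: a constant Type 1 hazard, equal in both arms, over 12 months from randomization. With control wait c and experimental wait e in months, the uncounted shares are c/12 and e/12, and the apparent experimental:control ratio is (1 − e/12)/(1 − c/12).

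| c vs e (months) | Uncounted, control | Uncounted, experimental | Apparent ratio |
|---|---|---|---|
| 2 vs 1 | 16.7% | 8.3% | 0.917/0.833 = 1.10 |
| 3 vs 1.5 | 25.0% | 12.5% | 0.875/0.75 = 1.17 |
| 6 vs 3 | 50.0% | 25.0% | 0.75/0.50 = 1.50 |

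The true ratio is 1.00 in each row.

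**Step 3. Numbers of events.** The arm sizes in section 9.1 are 187 control and 373 experimental. With waits of 3 vs 1.5 months the uncovered time is:

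- control: 187 × 3/12 = 46.8 patient-years
- experimental: 373 × 1.5/12 = 46.6 patient-years

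The expected numbers lost are therefore about equal. The protocol gives no MI rate for the wait. At an assumed 1% to 5% per patient-year, the loss is about 0.5 to 2.3 events in each arm, or 0.25% to 1.25% of controls and 0.13% to 0.63% of experimental patients. With 6 vs 3 months and 5% per patient-year it is 187 × 6/12 × 0.05 = 4.7 events in each arm.

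Only if the experimental wait is less than half the control wait does the control arm also lose more in number. With 3 vs 1 months, for example, the uncovered time is 187 × 3 = 561 against 373 × 1 = 373 patient-months.

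**Step 4. Longer horizon.** Follow-up runs to 3 years (7.5), and section 4.2 sets no 1-year limit for MI. Over 36 months the ratio is 34.5/33 = 1.05 for 3 vs 1.5 months and 33/30 = 1.10 for 6 vs 3 months.

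**The case against.** **The heading is only a divider.** The 48 h limit can be read as separating spontaneous from periprocedural infarction (Types 4A and 5). The diagnostic criteria under Type 1 carry no time limit of their own, and the endpoint is MI of any type. A sensible committee would probably call a thrombotic infarction in the wait spontaneous, and its charter may already say so. This makes a literal application less likely. But the written definition still excludes the event, and the committee should not have to depart from its text case by case in an open-label trial that relies on predetermined definitions.

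**The size is modest.** This stands. The ratios hold for Type 1 MI only. Types 2, 3, 4A to 4C and 5 are unaffected and dilute the effect on the endpoint by an amount that the protocol does not let us quantify. The halved wait is a supposition in the background, not a planned difference between the arms, and section 3 expects waits to shorten in the center with on-site surgery as well.

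**A reader might infer that more events are lost in the control arm.** The documents do not support that as a general statement. Under 2:1 allocation and a halved wait the expected counts lost are about equal, and only the proportion per patient differs.

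**Conclusion.** The gap is real on the text, but it is a minor point confined to a secondary endpoint. It affects non-fatal, non-stent-related Type 1 MI between randomization and TAVI. If the table is applied literally, the secondary MI comparison is biased against the experimental arm. The apparent ratio of 1.10 to 1.50 is an illustration for Type 1 MI alone and rests on the assumptions in the working. The likely loss is a few events at most.

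Two stronger readings are not supported. First, the non-inferiority result is not materially at risk: acute MI is among the other cardiovascular hospitalizations that section 8.12 brings into the primary endpoint, and every death counts. Second, the gap cannot make the experimental arm look better on MI when controls wait longer, because the undercounting then falls proportionally more on the controls.

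**What to change.** Add one sentence to section 8.16 and to the adjudication charter, in the manner of section 8.12: *For this study Type 1 MI also applies from randomization until the index TAVI procedure; events within 48 h after a PCI or after TAVI are classified by the Type 4A or Type 5 criteria respectively.*

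The second half is needed. If Type 1 were simply opened to the whole wait, an infarction within 48 h of a PCI done before TAVI could qualify at the 99th-percentile troponin threshold. It would then bypass the much higher Type 4A thresholds (CK-MB at least 10 times, or troponin at least 70 times, the upper limit of normal, or half those multiples with supporting findings), which would add spurious events during the wait.

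The cost is one sentence in each of two documents, best settled before adjudication of MI is complete. It needs no new data, visits or patients, since adverse events are already collected from randomization, and the sample size does not change.
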